5.10. Minimum sample size

The minimum sample size was estimated considering the variations of safety outcomes considered clinically relevant in the primary breast augmentation groups in different studies with a 3-year follow-up. It would be interesting to consider event risk estimates over 10 years because of the study follow-up plan. However, the risks available in the literature are rarely reported in 10 years or it is not possible to be sure that all volunteers have been followed for 10 years or more. It was possible to find only one study with a 9-year accumulated risk assessment with Silimed® products [36], which indicates that the risks of implant rupture are 4.3% and 1.2%, that the capsular contracture risks are 12.0% and 14.4%, that the risks of removal of the implant were 13.9% and 36.4%, and that the risks of any reoperation were 22.2% and 47.9%, always in the primary augmentation and primary reconstruction groups respectively. In this way, we also considered the risk accumulated in 3 years of previous studies that were used to register similar products and that the risks between the implant types are equivalent.

The events considered relevant were: need for reoperation for any reason, removal of the implant without replacement, removal of the implant with replacement, capsular contraction grade III or IV and implant rupture initially having a study of 3 years of follow-up and as a measure of interest to be estimated at a given time event, in the example of 3 years of follow-up. We used the epiDisplay package of R-project software that has a function with a formula that indicates the probability of the event of interest in the population and the formula returns the minimum sample size (N). [37] In addition, we determined the additional arguments of the formula, which are the population size for which the results would be inferred as infinity, the significance as 5%, and the difference between the estimated probability and one of the limits of the confidence interval (accuracy) as follows: if the probability to be estimated between 0.30 and 0.70, the desired accuracy = 0.1; If the probability is between 0.10 and 0.30, or between 0.70 and 0.90, the desired accuracy would be = 0.05; If the probability to be estimated is less than 0.10 or greater than 0.90, the desired accuracy would be half the probability or half of the probability respectively.

With the reoperation as a result, it was decided that the probability to be estimated could vary between 10% and 18%, which would lead to a minimum sample N of 138 to 227 volunteers. Still in the **Silimed Indústria de Implantes Ltda**

[name]

[contact] [contact]

www.silimed.com.br • [contact] • facebook: silimed international/brasil

same group having as an outcome the removal of the implant without replacement, it was decided that the probability to be estimated could vary between 0.5% and 3% which would take the minimum sample N between 3099 and 558. For the implant removal outcome with replacement, it was judged that the probability to be estimated could range from 5% to 25% by making the minimum sample N vary between 81 and 753 still in the primary augmentation group. As for the capsular contracture outcome, it was estimated that the probability to be estimated could vary between 2% and 10%, making the minimum sample N vary between 138 and 753.

Considering that the study will follow a larger follow-up than the example above, and that the risk of these events will accumulate, and that the highest and lowest risk of events observed in 9 years were respectively 1.2% and 47.9 % [36], the minimum sizes for desired accuracy in the primary augmentation groups would be 246 volunteers, that is, 246 volunteers in the textured implant group and other 246 in the polyurethane implant group. Finally, if we consider a loss of follow-up of 40% over 10 years, the total sample size should be increased from 492 to 700 (proportionally distributed between the 2 groups). In conclusion, a sample of 350 volunteers in the textured implant group and another 350 in the polyurethane implant group.

In the event of loss of follow-up greater than planned, there will be no replacement, i.e. there will be no further inclusions or substitutions throughout the study, nor interruption of the study. In this case, it must be considered if the loss of follow-up is differential, which may lead to errors in the final estimates of greater interest, or non-differential, and may only lead to loss of precision in the estimates. In the first case, since the outcome in the observed period will be unknown, it would be reasonable to explore the possibilities of uninterrupted participants presenting and not presenting the outcomes of interest, and in these two scenarios to see if there are relevant differences that modify the interpretation. In the second case, what should occur is the loss of accuracy of the estimates beyond that expected in the period after the loss of follow-up is greater than expected. Vagueness may disrupt the interpretation of results in the final periods of observation but will not invalidate interpretation in previous periods.

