2.3. Expectation of expected adverse events

Technical reports provided by the FDA used for silicone breast implant registries from different manufacturers indicate a variety of risks from implant or surgery-related events. The most frequent event in all reports, consistent with the literature in general, is capsular contracture. Capsular contracture, when intense, is also the most frequent indication of implant removal. Below is a comparison of risks of events of interest by major interest groups and by different manufacturers. However, it is not possible, through the data from these reports to verify if there are differences between the different types of implants, nor what prognostic elements determine

Silimed Indústria de Implantes Ltda

[name]

[contact] **[contact]

www.silimed.com.br • [contact] • facebook: silimed international/brasil

the events in the different interest groups.

Cumulative incidence by type of event, implantation indication and implant brand (data retrieved from technical registration reports).

	Natrelle (Textured Surface - in 7 years)%		Natrelle (Textured Surface - in 3 years)%		Sientra (any surface - in 3 years)%		Mentor (any surface - in 3 years)%	
Event	Augmentation	Reconstruction	Augmentation	Reconstruction	Augmentation	Reconstruction	Augmentation	Reconstruction
Any Complication	31,0	53,0	-	-	-	-	-	-
Any Reoperation	22,4	45,2	12,7	21,0	12,6	34,9	15,4	27,0
Removal of the implant with or without replacement	12,6	29,3	-	-	-	-	-	-
Removal of the implant without replacement	1,2	5,3	0,5	2,9	1,2	7,0	2,3	5,7
Removing the Implant with Replacement	11,5	25,2	5,0	14,9	4,6	19,1	2,8	7,4
Capsular contracture grade III / IV	6,1	10,7	2,1	7,3	6,0	8,8	8,1	8,3
Implant rupture	6,9	8,9	1,3	0,0	3,0	0,0	0,0	0,0

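### Section 5.10: three of the eight event-specific minimum sample sizes, all for implant removal, do not follow from the plan's own accuracy rule, and the 25% upper risk for removal with replacement has no support in the augmentation data

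*Combined protocol and SAP*

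**What the plan says.** Section 5.10 sizes the study by the precision of a single estimated risk. The software is named ("We used the epiDisplay package of R-project software that has a function with a formula"), significance is set at 5%, and the population is taken as infinite ("the population size for which the results would be inferred as infinity"). The half-width depends on the risk: "if the probability to be estimated between 0.30 and 0.70, the desired accuracy = 0.1"; 0.05 from 0.10 to 0.30; and, for a risk "less than 0.10 or greater than 0.90, the desired accuracy would be half the probability".

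The rule is then applied to four events in primary augmentation, using 3-year follow-up as the example:

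- Reoperation, 10% to 18%: N of 138 to 227.
- Removal without replacement: "probability to be estimated could vary between 0.5% and 3% which would take the minimum sample N between 3099 and 558".
- Removal with replacement: the risk "could range from 5% to 25% by making the minimum sample N vary between 81 and 753".
- Capsular contracture, 2% to 10%: N of 138 to 753.

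The section then turns to longer follow-up, adopts 246 per group as the minimum for the desired accuracy, and raises this to 350 per group for 40% loss over 10 years.

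**The concern.** The 81 to 753 given for removal with replacement is implausible on its face. The upper figure equals the one given for capsular contracture at 2%, although the stated risk starts at 5%. A range reaching 25% is also hard to square with the row "Removing the Implant with Replacement" in the table of section 2.3, where the only value near 25% belongs to reconstruction, an indication that this study does not enrol.

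Removal is among the events of greatest interest in the executive summary and supplies two of the three alarm outcomes in section 5.11. Section 5.10 is where a reader looks to learn how precisely those risks will be estimated. If its figures do not follow from its own rule, the reader cannot tell which accuracy targets the study meets.

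**Working it through.** **Inputs.** From section 5.10: 5% significance (two-sided, z = 1.96), infinite population, and half-width d = p/2 for p below 0.10, 0.05 for 0.10 to 0.30, and 0.10 for 0.30 to 0.70. From section 2.3, removal with replacement in augmentation: 5.0%, 4.6% and 2.8% at 3 years; 11.5% at 7 years.

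**Formula.** n = 1.96² × p(1 − p) / d².

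**The plan's figures against the rule.** For removal with replacement the plan does not say which N belongs to which end; 753 is set against 5% and 81 against 25%.

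| Event | p | d | N by rule | N stated |
|---|---|---|---|---|
| Reoperation | 10% | 0.05 | 138.3 | 138 |
| Reoperation | 18% | 0.05 | 226.8 | 227 |
| Capsular contracture | 2% | 0.01 | 752.9 | 753 |
| Capsular contracture | 10% | 0.05 | 138.3 | 138 |
| Removal without replacement | 0.5% | 0.0025 | 3057.8 | 3099 |
| Removal without replacement | 3% | 0.015 | 496.8 | 558 |
| Removal with replacement | 5% | 0.025 | 292.0 | 753 |
| Removal with replacement | 25% | 0.05 | 288.1 | 81 |

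The first four rows reproduce, so this is the formula the plan used. The 3099 is 1.3% high (3099/3058 = 1.013), which is small. The 558 is 12% high (558/497 = 1.12).

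For removal with replacement, pairing does not matter. Between 5% and 10% the required N falls from 292 to 138, and between 10% and 25% it rises to 288. Nothing in the stated range gives 81 or 753. Those are the Ns for 30% with d = 0.10 (80.7) and for 2% (752.9).

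**Could another formula explain it?** One-sided and 99% versions, continuity correction, Wilson and Clopper-Pearson widths were tried. None reproduces both ends of either removal range. Continuity correction gives 561.5 at 3%, close to 558, but it gives 3446 at 0.5%, 850 at 2% and 158 at 10%, contradicting 3099, 753 and 138.

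**The risk range.** The augmentation values are 2.8% to 5.0% at 3 years and 11.5% at 7 years. Removal of any kind at 9 years is 13.9% (section 5.10). The 25.2% in section 2.3 is reconstruction at 7 years. Even the 10-year alarm limit for this event in section 5.11 is 18.10%. The 5% lower end leaves out 4.6% and 2.8%, where the rule asks for more patients. By the rule: 533 at 2.8%, 319 at 4.6%, 292 at 5.0%, 156 at 11.5%.

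**Precision delivered.** Half-width = 1.96 × √(p(1 − p)/n), in percentage points:

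| Event | p | Rule | n = 246 | n = 350 |
|---|---|---|---|---|
| Removal without replacement | 0.5% | 0.25 | 0.88 | 0.74 |
| Removal without replacement | 3% | 1.5 | 2.13 | 1.79 |
| Removal with replacement | 2.8% | 1.4 | 2.06 | 1.73 |
| Removal with replacement | 5.0% | 2.5 | 2.72 | 2.28 |
| Removal with replacement | 11.5% | 5 | 3.99 | 3.34 |

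Below 10% the required N falls as p rises, so the least demanding point in 0.5% to 3% is 497 at 3%. That exceeds both 246 and 350.

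**The case against.** The strongest reply is that nothing in the design rests on these figures. Section 5.10 presents the 3-year calculation as an example and then moves to longer follow-up. The adopted 246 does not come from the removal ranges; it matches the rule at 20% with ±5 points (245.9). Correcting three numbers leaves 350 per group where it was. This stands.

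A reader might infer that the plan claims better precision for removal than it delivers. The documents do not support that. Section 5.10 gives no half-width for removal, only required Ns. Two of the three wrong Ns, 558 and 753, err high; only 81 errs low. The stated 3099 and 558 already exceed 350, so the shortfall for removal without replacement was visible without any correction.

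A reader might also take the 210 per group left after 40% loss (350 × 0.6) and conclude that removal with replacement misses the rule even at 5.0% (±2.95 against 2.5). That pairs a 3-year risk with 10-year loss. If loss were constant over time, which is an assumption, about 300 would remain at year 3 (350 × 0.6^0.3 = 350 × 0.858), more than the 292 needed at 5.0%. The planned Kaplan-Meier estimate also uses follow-up from participants lost later. The 210 is useful only as a conservative bound for late risks, and there the rule is met: ±4.3 at 11.5%, against 5.

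Finally, the plan's range is a judgement, and replacing it with 2.8% to 5.0% alone would drop the 7-year augmentation value of 11.5%. This also stands. Since 81 and 753 are exact Ns for 30% and 2%, the slip may lie in the range rather than in the Ns. The documents therefore call for reconciliation, not one forced substitution.

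**Conclusion.** The point holds as an internal inconsistency of minor severity; the text is wrong as written. Three of eight Ns fail the plan's own rule: 558 should be 497, and 81 to 753 should be 138 to 292 if 5% to 25% is kept. The 25% bound has no support in the augmentation data.

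The size of the study is not shown to be wrong by this. What section 5.10 should not leave standing is the impression that 246 per group gives the desired accuracy for the removal events. The half-of-risk accuracy is missed for removal without replacement anywhere in 0.5% to 3%, at 246 or 350 per group, and for removal with replacement at 2.8%. At 350 it is met at 4.6%, 5.0% and 11.5%.

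The result rests on the two-sided 95% normal-approximation formula, which the four reproduced figures support, and on all 350 contributing. At 0.5% only 350 × 0.005 = 1.75 events are expected, so ±0.74 serves for comparison with the rule, not as a usable interval.

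**What to change.** In section 5.10:

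1. For removal without replacement, replace 558 by 497 and, for consistency, 3099 by 3058.
2. For removal with replacement, reconcile the range and the Ns. Preferably use an augmentation-based range with matching Ns: 533 at 2.8%, 319 at 4.6%, 292 at 5.0% and 156 at 11.5% (7 years). If 5% to 25% is kept, give 138 to 292 and justify the upper bound for augmentation.
3. State the half-widths delivered at 350 per group: ±0.74 at 0.5% and ±1.8 at 3% for removal without replacement; ±1.7 at 2.8% and ±2.3 at 5.0% for removal with replacement.
4. Say plainly that the half-of-risk accuracy is not met for removal without replacement in 0.5% to 3%, nor for removal with replacement at 2.8%.
5. If precision after 40% loss is shown, use 210 per group only as a conservative bound for late risks.

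The cost is wording and numbers in one section. No patients are added, and no analysis or alarm limit changes.

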5.3.1. Inclusion Criteria

Inclusion criteria: (1) provide free informed consent, (2) female at birth, (3) 18 years or older, (4) have received breast implant(s) for indication of primary augmentation up to 14 days prior, (5) have received breast implants with a textured surface or breast implant with a polyurethane foam-coated surface of the brand Silimed®, (6) ability to comply with the protocol for the entire follow-up time.

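### The base size of 246 per group in section 5.10 has no stated basis and cannot be reproduced from the accuracy rule at any cited 9-year risk; the two risks beside it come from reconstruction patients

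*Combined protocol and SAP*

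**What the plan says.** Section 5.10 sizes the study by the precision of a single proportion, at 5% significance and for an infinite population. The accuracy wanted, meaning the distance from the estimate to one confidence limit, depends on the risk p. It is 10 points for p from 30% to 70%, and 5 points for 10% to 30% or 70% to 90%. For small risks, "If the probability to be estimated is less than 0.10 or greater than 0.90, the desired accuracy would be half the probability".

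The section cites one 9-year study with four pairs of risks: rupture 4.3% and 1.2%, contracture 12.0% and 14.4%, removal 13.9% and 36.4%, reoperation 22.2% and 47.9%. The order is "always in the primary augmentation and primary reconstruction groups respectively". The relevant events include "capsular contraction grade III or IV and implant rupture initially having a study of 3 years of follow-up", but the 3-year example sizes that follow omit rupture.

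The section then says that "the highest and lowest risk of events observed in 9 years were respectively 1.2% and 47.9 % [36"] and that "the minimum sizes for desired accuracy in the primary augmentation groups would be 246 volunteers" in each implant group. Next, "if we consider a loss of follow-up of 40% over 10 years, the total sample size should be increased from 492 to 700", which gives 350 per group. Section 5.3.1 admits only women who "have received breast implant(s) for indication of primary augmentation up to 14 days prior".

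**The concern.** A sample size based on precision should be traceable to a named risk and a named accuracy. Here neither is stated for 246, and the two risks quoted beside it belong to an indication that the trial does not enrol. A reader cannot tell which event the study was sized for. The primary analysis consists of risk estimates with confidence intervals, so expected interval width is the only statistical case for the sample size. If 246 does not deliver the accuracy claimed, readers will credit the study with more precision for some events than that size gives.

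**Working it through.** **Formula.** n = z² p(1 − p)/d², with z = 1.96 (two-sided 5%) and d from the rule in 5.10. The section does not state sidedness; two-sided is inferred from the check that follows.

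**Reproducing the plan's own figures.**
- 10%, d = 5 points: 3.8416 × 0.09/0.0025 = 138.3 (plan: 138)
- 18%, d = 5 points: 3.8416 × 0.1476/0.0025 = 226.8 (plan: 227)
- 2%, d = 1 point: 3.8416 × 0.0196/0.0001 = 753 (plan: 753)

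**All eight 9-year risks in 5.10.**

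| Event | Augmentation p | d (points) | n | Reconstruction p | d (points) | n |
|---|---|---|---|---|---|---|
| Rupture | 4.3% | 2.15 | 342 | 1.2% | 0.6 | 1,265 |
| Contracture | 12.0% | 5 | 162 | 14.4% | 5 | 189 |
| Any removal | 13.9% | 5 | 184 | 36.4% | 10 | 89 |
| Reoperation | 22.2% | 5 | 265 | 47.9% | 10 | 96 |

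None is 246.

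**What would give 246.**
- 20% with 5 points: 3.8416 × 0.16/0.0025 = 245.9.
- About 5.9% with p/2: 4 × 3.8416 × (1 − 0.0588)/0.0588 = 246.0.
- Section 5.10 states neither as its basis.
- A one-sided 5% calculation at 4.3% comes near, at 241. But one-sided gives 97 at 10%, where the plan has 138, so it is not the plan's convention.
- The midpoint of 1.2% and 47.9% (24.55%) gives 285. The mean of the four augmentation sizes is 238.

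**Precision delivered.** Half-width = 1.96 √(p(1 − p)/n), in percentage points, for the 9-year augmentation risks:

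| Event | Rule | n = 246 | n = 350 | n = 210 |
|---|---|---|---|---|
| Rupture 4.3% | 2.15 | 2.53 | 2.13 | 2.74 |
| Contracture 12.0% | 5.00 | 4.06 | 3.40 | 4.40 |
| Any removal 13.9% | 5.00 | 4.32 | 3.62 | 4.68 |
| Reoperation 22.2% | 5.00 | 5.19 | 4.35 | 5.62 |

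The 210 is 350 × 0.6, the completers at the planned 40% loss.

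**Removal without replacement (3-year range in 5.10).** The rule needs about 3,058 at 0.5% and 497 at 3%. At 350 the half-width at 3% is 1.96 √(0.03 × 0.97/350) = 1.79 points against 1.50. At 0.5% it is 0.74 against 0.25.

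**Neighbouring figures in 5.10.**
- 3% with 1.5 points gives 496.8; the plan prints 558.
- For removal with replacement at 5% to 25%, the rule gives 292 at 5%, 138 at 10% and 288 at 25%, so about 138 to 292. The plan prints 81 to 753, which are the rule's values at 30% (10 points: 80.7) and at 2%.
- Loss step: 492/0.6 = 820, whereas 1 − 492/700 is a loss of 29.7%.

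**The case against.** The strongest reply is that 5.10 never says 246 was calculated at 1.2% or 47.9%. They can be read as a bracket for how far risks might accumulate, with a round value chosen inside it. A 20% risk with 5 points gives 246 almost exactly and lies just above the 10% to 18% assumed for 3-year reoperation. This reply stands in part. A reader might infer that the sponsor put the reconstruction risks into the formula, but the text does not support that, and the resulting 1,265 and 96 show they were not used directly. That 20% was the basis is equally an inference. What remains is that no basis is stated and that the bracket comes from the wrong indication.

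A second reply is that little depends on 246. The study is estimative, 350 are enrolled per group, and the misses at 246 are 0.19 points for reoperation and 0.38 for rupture. That is correct, and it limits the weight of the point.

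Third, the shortfall for removal without replacement is already visible, since 5.10 prints sizes of 3099 and 558 for it. Also true, although the later claim for 246 makes no exception for that event.

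Fourth, 210 completers understate the information, because the Kaplan-Meier estimate planned in 5.9 uses follow-up up to censoring. This stands, so the 210 column is a conservative bound. Loss beyond 40% would worsen it, and "In the event of loss of follow-up greater than planned, there will be no replacement".

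**Conclusion.** The point holds as a defect in the stated justification. The figure of 246 has no stated basis and does not follow from the plan's rule at any 9-year risk it cites. The 1.2% and 47.9% are rupture and reoperation in reconstruction; the augmentation extremes are 4.3% and 22.2%. The value 1.2% also appears in the table in section 2.3 for removal without replacement after augmentation, but 5.10 ties its figure to the 9-year study.

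Meeting the rule at all four augmentation risks takes 342 per group, 39% more than 246. Reoperation alone takes 265, 8% more.

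Two stronger readings are not supported. A reader might infer that the enrolled sample is too small, but 350 with no loss meets the rule for all four risks. A reader might also infer that 246 works only for risks of about 5.9% to 20% and 30% to 70%; the rule has a further 5-point band at 70% to 90%, and 246 meets it from 80% upward.

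The result assumes two-sided 95% intervals, the normal approximation, and the risks as quoted in 5.10.

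**What to change.** Reword 5.10 and keep 350 per group:

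1. Replace 1.2% and 47.9% with the augmentation range, 4.3% to 22.2%.
2. Either state the risk and accuracy that give 246, or withdraw 246 and justify 350 by its expected precision.
3. Print the expected half-widths for the four 9-year augmentation risks at 350 (no loss) and at 210 (completers at 40% loss, labelled as a conservative bound), as tabulated above.
4. Say that the rule is not met for removal without replacement. Label the time horizon and source of any 3-year or 7-year risk shown, and do not pair 3-year risks with 10-year completers.
5. If 246 is kept, reconcile the step from 492 to 700 with 40% loss. If 246 is withdrawn, that step goes with it.
6. Correct 558 at 3% to about 497, and reconcile 81 to 753 with its stated 5% to 25% range (about 138 to 292).

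The cost is a rewritten paragraph and one small table, with no change to enrolment or analysis. The stated precision becomes less favourable for rare events, and without 246 the case for 350 rests on expected precision alone.

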5.9. Statistical analysis plan

The statistical analysis will be divided into two parts, one descriptive and one analytical. The descriptive part will consist of showing counts and fractions of categorical variables and central tendencies (mean + standard deviation or median + interquartile range) of continuous variables recorded at the beginning of the follow-up by the groups of major interest. The groups of major interest are formed by the indication of implantation and the type of implant (primary augmentation
Silimed Indústria de Implantes Ltda

[name]

[contact] **[contact]

www.silimed.com.br • [contact] • facebook: silimed international/brasil

with textured surface implant, primary augmentation with polyurethane foam-coated surface implant). In addition, for the purpose of exploring heterogeneity this approach will also be done by participant center.

The initial statistical analysis for the analytical part is to estimate the risks (cumulative probabilities up to a follow-up time) and their respective confidence intervals of unwanted (expected and not expected) events in general and interest-specific ones (e.g. capsular contracture in the textured implants group, in the polyurethane implants group, mild events, serious events, events with probable causality, etc.), as well as events of different intensities (mild, moderate, severe, etc.). The accumulated risks up to the first events in the period of interest will be estimated through the Kaplan-Meier estimator. This analysis should consider the patient as an observation unit, and then the same approach will consider the breast as an observation unit.

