The names and identities of the participants will be kept confidential by the Principal Investigator and his/her team and by the research monitor. No information will be provided outside the research center without the participant's permission. The data entry system has a series of controls and rules that prevent incoming out-of-format data, inconsistent data, and blank field submission. As well as a monitoring and calling tool for checking extreme, unusual or unverified data. Even so, professionals must be able to properly fill out data collection forms, since data entry essentially minimizes typing errors and not fill-in errors.

13. Expected outcomes

It is expected from this investigation that Silimed® products are of similar safety or safer than literature data indicate, when compared to the results of the Silimed® products themselves prior to commercialization, or when compared to results of similar products from competing manufacturers. That could elucidate which groups of patients could be at greater risk of adverse events or that allow to discuss in what moments/conditions there could be additional interventions to reduce the known events. In addition, the beneficial effect of the implants is expected to be equivalent to or above a desired measure.

Silimed Indústria de Implantes Ltda

[name]

[contact] **[contact]

www.silimed.com.br • [contact] • facebook: silimed international/brasil

14. Execution Schedule:

Activities and indicators of progress	Time				
	2017	2018	2019	2020 to 2028	2029
- Submission of the project to the IRB	X	X			
- Inclusion of patients after approval of the research project by the Research Ethics Committee and notification to ANVISA		X	X*		
- Presentation of the partial analysis of the data collected			X	X	
- Presentation of the final analysis of the data collected					X

* If the total number of participants is not reached in the year 2018, the recruitment may be extended until 2019. After the "N" of the study (700 participants in total) is reached, the inclusion will be interrupted, not being possible to include any volunteer, not even in case of loss of follow-up throughout the study.

Silimed Indústria de Implantes Ltda

[name]

[contact] [contact]

www.silimed.com.br • [contact] • facebook: silimed international/brasil

15. Bibliography

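### Section 5.10 presents 700 women as covering 40% loss to follow-up, but 350 per group less 40% is 210, below the required 246; 700 covers about 30% loss

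*Combined protocol and SAP*

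**What the plan says.** Section 5.10 sizes the study for precision. It uses a single-proportion formula at 5% significance, with the accuracy target depending on the size of the risk. After a set of 3-year examples it moves to long-term risks and arrives at "246 volunteers in the textured implant group and other 246 in the polyurethane implant group". It then allows for attrition: "if we consider a loss of follow-up of 40% over 10 years, the total sample size should be increased from 492 to 700", and concludes with "a sample of 350 volunteers in the textured implant group and another 350 in the polyurethane implant group". It gives no inflation formula and no other loss rate.

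The same section closes off later correction: "In the event of loss of follow-up greater than planned, there will be no replacement", and "there will be no further inclusions or substitutions throughout the study". The footnote to the schedule in section 14 repeats this: once 700 is reached, "the inclusion will be interrupted, not being possible to include any volunteer, not even in case of loss of follow-up throughout the study".

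For the analysis, section 5.9 states: "The accumulated risks up to the first events in the period of interest will be estimated through the Kaplan-Meier estimator".

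**The concern.** To have a given number left after a fraction d is lost, one divides by (1 − d). Going from 492 to 700 is a factor of 1.42, whereas 40% loss calls for 1/0.60 = 1.67. The sentence therefore claims more protection against loss than the sample size gives.

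Two things follow. No participants can be added later, so a shortfall at year 10 would stand. Also, section 5.10 ties any unexpected loss of precision to attrition beyond the plan, which a reader will take to mean above 40%. On the plan's own sizing the margin is used up at about 30%. Loss between 30% and 40% would be reported as within plan while fewer than 246 women per group complete follow-up.

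**Working it through.** **Inputs from section 5.10:** 246 per group (492 in total); 40% loss over 10 years; 700 enrolled (350 per group); 5% significance; target half-width 0.05 for risks between 0.10 and 0.30, half the risk below 0.10, and 0.10 for risks between 0.30 and 0.70.

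**Reproducing 246.** n = 1.96² p(1 − p)/d².
- p = 0.20, d = 0.05: 245.9, so 246. The plan does not state the 20%; it is inferred here.
- The two 9-year risks cited beside the figure do not give it. 1.2% (d = 0.006) needs 1,266 and 47.9% (d = 0.10) needs 96.

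**Reproducing 700.**
- 492 × 1.40 = 688.8, close to 700 after rounding up. This adds 40% to the target, which does not leave the target once 40% are lost.
- 492/0.70 = 702.9, also close to 700, but this is 30% loss.
- 492/0.60 = 820, the figure that matches the stated 40%.

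The plan does not say which route was taken.

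**What 350 per group gives.**
- Remaining after 40% loss: 350 × 0.60 = 210, which is 36 (15%) below 246.
- Needed per group for 40% loss: 246/0.60 = 410.
- Largest loss that keeps 246: 1 − 246/350 = 29.7%.

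**Precision as a simple proportion.** At p = 0.20 the 95% half-width is 1.96 × √(0.16/n): 5.00 points with 246 and 5.41 with 210.

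**Precision with Kaplan-Meier.** Women who are lost contribute until censoring. Assume a 10-year risk of 20% with constant event hazard h = −ln(0.8)/10, n = 350, and 40% lost at a constant hazard c = −ln(0.6)/T up to year T, with none lost after. Greenwood variance at year 10 is S² × ∫ h/(n S(t) G(t)) dt, where S is event-free survival and G is retention. Effective n is 0.16/variance.

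For T = 10: h = 0.0223 and c = 0.0511. The integral apart from n is h/(h + c) × (1/(0.8 × 0.6) − 1) = 0.3040 × 1.0833 = 0.3294. Variance = 0.64 × 0.3294/350 = 0.000602. Half-width = 4.81 points and effective n = 265.7.

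| Loss completed by year | Effective n | Half-width (points) |
|---|---|---|
| 10 | 265.7 | 4.81 |
| 7 | 245.1 | 5.01 |
| 5 | 233.5 | 5.13 |
| 3 | 223.3 | 5.25 |
| 1 | 214.2 | 5.36 |

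A simulation with 4,000 replicates (Monte Carlo error about 2%) gave effective n of 265, 248, 226 and 214 for T = 10, 7, 5 and 1.

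**Does the shortfall change whether a target is met?** Required n at the four 9-year primary-augmentation risks in section 5.10:

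| Event | Risk | Required n | Met with 246 | Met with 210 |
|---|---|---|---|---|
| Contracture | 12.0% | 163 | yes | yes |
| Removal | 13.9% | 184 | yes | yes |
| Reoperation | 22.2% | 266 | no | no |
| Rupture | 4.3% | 342 | no | no |

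None moves from met to missed; half-widths widen by 0.2 to 0.4 points. The only n that section 5.10 itself states between 210 and 246 is 227 (reoperation at 18%). That is a 3-year risk, and even loss would leave 350 × 0.6^0.3 ≈ 300 per group at 3 years.

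**The case against.** The strongest reply is that 246 is a number for a desired accuracy, not a number of women who must still be attending at year 10. With Kaplan-Meier and loss spread evenly over the 10 years, arguably the natural reading, 350 per group gives an effective n of about 266 and a half-width of 4.8 points, so the target is met. If events come early, as section 2.3 suggests for contracture, the position improves. With half of the cumulative event hazard in the first 3 years (an assumption), effective n is about 279. At 9 years with even loss, effective n for reoperation at 22.2% is about 273, above the 266 required. The study is descriptive, and no test or power claim rests on 246, a figure whose own basis is not explained.

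Most of this stands, and it limits the consequence. It does not make the sentence correct. The sizing formula in section 5.10 is for a simple proportion and takes no credit for censored follow-up, and the section makes no such argument. The reply also depends on when loss occurs, which the plan does not state: on the constant-hazard calculation the target is just missed if all loss falls within about 7 years. The incidence by year of follow-up and the questionnaire means in section 5.9 rest at year 10 on the women still under observation, although 246 was not sized for those analyses.

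A second point concerns the number 210. Section 6.5.1 lists implant removal or replacement as a possible reason for withdrawal, separately from loss to follow-up. If all women with removal (13.9% by 9 years) were withdrawn in addition to the 40%, independently of it, about 210 × 0.861 = 181 per group would remain. The 210 therefore holds only if 40% is the total from all causes.

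**Conclusion.** The concern holds. The statement that 700 allows for 40% loss is arithmetically wrong: it leaves 210 per group rather than 246, and the sample covers 29.7% loss. These figures need nothing beyond section 5.10.

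The cost in precision is small, at most about 0.4 of a percentage point. It rests on an inferred 10-year risk of 20% and, for Kaplan-Meier, on a constant event hazard and the timing of loss: the 5-point target is met with even loss and missed with early loss. The study is not invalidated. The sentence should be corrected because it gives an assurance about attrition that the sample size does not support, and the plan excludes later enrolment.

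**What to change.** Keep 700 and correct the sentence in section 5.10.

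**Preferred:** keep the 40% assumption and state what it implies, for example:

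> With 350 per group and 40% total loss over 10 years, about 210 per group are expected to be followed to year 10. At an assumed 10-year risk of 20%, the Kaplan-Meier 95% half-width is about 4.8 percentage points if loss is even over 10 years and up to 5.4 points if loss is early (target 5.0).

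The sentence should say that the 40% includes withdrawals of every kind. The paragraph on loss beyond the plan then needs no change.

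**Alternative, with no assumed risk:** state that 700 preserves 246 per group only up to about 30% loss, and define loss beyond the plan in that paragraph as above 30%.

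Either way the cost is one sentence, plus one clarifying phrase under the alternative. There are no extra participants and no change to the design; one stated figure becomes slightly less favourable. Preserving 246 per group under 40% loss would instead take 820 women, 120 more, which the modest loss of precision does not call for.
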